2.5.3 Handling of missing values/censoring/discontinuations

The analysis will be performed based on all available data in the FAS and based on likelihood method with an assumption of missing at random for missing data.

2.5.4 Supportive analyses

The primary endpoint will be analyzed in the FAS using the same analytical approach as described in Section 2.5.2; however, baseline will be defined as the last non-missing NT-proBNP assessment with collection date:time < first dose date:time.

For NT-proBNP at Weeks 4 and 8, a proportional change from baseline in a logarithmic scale will be analyzed using an ANCOVA model with treatment as a fixed effect factor and the logarithmic baseline biomarker value as a covariate. For each visit, the estimated treatment effects in terms of ratios of the geometric means based on the LS means from the model and the corresponding two-sided 95% confidence intervals produced from the model will be presented. The geometric mean will be calculated by exponentially back transforming the LS means.

The primary endpoint will also be analyzed in the PPS using the same analytical approach as described in Section 2.5.2.

In addition, a binary outcome variable will be created for patients achieving a 25%, 50% and 75% decline in NT-proBNP (0-no, 1-yes) and a logistic regression model will be fit. The odds ratio, 95% confidence interval and p-value will be provided. The outcome variable will be achieving a decline in NT-proBNP and the predictor of response will be treatment group.

A descriptive summary of patient evaluability for the primary endpoint analysis based on NT-proBNP values will be presented by treatment group.

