2.5.2 Statistical hypothesis, model, and method of analysis

The primary hypothesis to be tested is the ratio of the geometric means of NT-proBNP (average of Weeks 4 and 8/baseline) for the sacubitril/valsartan and enalapril treatment groups are equal (H0) versus the ratio of the geometric means of NT-proBNP are not equal(Ha).

For NT-proBNP, the time-averaged proportional change from baseline in a logarithmic scale will be analyzed using an analysis of covariance (ANCOVA) model using data from Weeks 4 and 8 with treatment as a fixed effect factor and the logarithmic baseline biomarker value as a covariate.

The values from Weeks 4 and 8 will be averaged and the change from baseline in log-transformed NT-proBNP will be calculated as follows:

log (average post dose value) – log (baseline value)

The estimated treatment effect in terms of ratios of geometric means, based on the least-squares (LS) means from the model, and the corresponding two-sided 95% confidence intervals will be presented.

The geometric means (presented as a ratio to baseline) will be calculated by exponentially back transforming the LS means based on the ANCOVA model as follows:

exp (LS mean)

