2.7.2 Statistical hypothesis, model, and method of analysis

For NT-proBNP at Week 8, a proportional change from baseline in a logarithmic scale will be analyzed using an ANCOVA model with treatment as a fixed effect factor and the logarithmic baseline biomarker as a covariate. The estimated treatment effects in terms of ratios of geometric means, based on the LS means from the ANCOVA model, and the corresponding two-sided 95% confidence intervals will be provided. Baseline is Week 0. Week 4 will be used if the Week 8 value is missing.

The incidence of symptomatic hypotension up to Week 8 will be calculated by treatment group. The relative risk (sacubitril/valsartan vs. enalapril) and the 95% confidence interval will also be presented. Similarly, the incidence of hyperkalemia, all angioedema, and positively adjudicated angioedema during the 8 week double-blind phase and the relative risk (sacubitril/valsartan vs. enalapril) will be summarized. Additionally, medication change, lowest documented systolic blood pressure and lowest documented diastolic blood pressure will be summarized by treatment group for symptomatic hypotension. The highest potassium value documented for hyperkalemia will also be summarized by treatment group.

For biomarkers including BNP, BNP to NT-proBNP ratio, NT-proBNP to BNP ratio, hs-Troponin T, UcGMP, and UcGMP to urinary creatinine ratio, the time-averaged proportional change from baseline in a logarithmic scale will be analyzed using an ANCOVA model using data from Weeks 4 and 8 with treatment group as a fixed effect factor and the logarithmic baseline biomarker value as a covariate.

Similar to the primary endpoint, the values from Weeks 4 and 8 will be averaged and the change from baseline will be calculated.

The estimated treatment effect in terms of ratios of geometric means, based on the LS means from the model, and the corresponding two-sided 95% confidence intervals will be presented. The geometric means (presented as a ratio to baseline) will be calculated by exponentially back transforming the LS means based on the ANCOVA model.

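### The 25/50/75% NT-proBNP responder models leave out log baseline, which every other visible NT-proBNP model adjusts for, so their test has less power than it could

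*SAP*

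**What the plan says.** In SAP 2.5.4, "a binary outcome variable will be created for patients achieving a 25%, 50% and 75% decline in NT-proBNP". A logistic model is fitted to each and gives an odds ratio, a 95% confidence interval and a p-value. On covariates the section says only that "the predictor of response will be treatment group". It names no visit for the decline.

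The other NT-proBNP models visible in the SAP all adjust for baseline:

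- Primary analysis (SAP 2.5.2): ANCOVA "with treatment as a fixed effect factor and the logarithmic baseline biomarker value as a covariate".
- Repeat of the primary analysis with a stricter baseline definition (SAP 2.5.4): same approach as 2.5.2.
- Per-protocol repeat (SAP 2.5.4): "The primary endpoint will also be analyzed in the PPS using the same analytical approach as described in Section 2.5.2".
- By-visit analysis (SAP 2.5.4): "For NT-proBNP at Weeks 4 and 8, a proportional change from baseline in a logarithmic scale will be analyzed using an ANCOVA model", again with log baseline as covariate.
- Secondary endpoint at Week 8 (SAP 2.7.2): the same ANCOVA form.

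Protocol 9.4.4 had planned unadjusted t-tests at Weeks 4 and 8. SAP section 4 records that they were replaced by ANCOVA. The visible text of protocol 9.4.4 contains no responder analysis.

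**The concern.** Whether a patient reaches a given percentage fall is likely to depend on the starting value, through regression to the mean and because a high value has more room to fall. That is the usual reason to adjust a change score for baseline, and the SAP follows it elsewhere, even where the protocol did not. The responder models are the visible exception, and no reason is given.

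What is at stake is the sensitivity of a supportive result. If log baseline predicts response, the treatment-only test is more likely to miss a real difference than a test that uses information already in hand. Results from three responder thresholds will be read beside the primary result, and an avoidable non-significant finding there would be awkward to explain.

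**Working it through.** **1. Reproduce the plan's figure.** Inputs from SAP section 3 and protocol 9.7: enalapril ratio to baseline 0.95, 18% relative reduction, SD 0.85 (log scale), two-sided alpha 0.05, power 85%, 25% non-evaluable.

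- Log difference: −ln(0.82) = 0.1985.
- n per arm = 2 × 0.85² × (1.960 + 1.036)² / 0.1985² ≈ 330 (331 with the t distribution).
- Total: 660/0.75 = 880, or 662/0.75 ≈ 883. The stated 882 is reproduced.
- Evaluable per arm: 882 × 0.75 / 2 ≈ 331.

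**2. Response rates implied by the design.** With log change normal, P(response) = Φ{[ln(1 − threshold) − mean]/0.85}. The mean is ln(0.95) = −0.0513 for enalapril and ln(0.95 × 0.82) = −0.2497 for sacubitril/valsartan.

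| Decline | Enalapril | Sacubitril/valsartan | Odds ratio |
|---|---|---|---|
| 25% | 39.0% | 48.2% | 1.45 |
| 50% | 22.5% | 30.1% | 1.48 |
| 75% | 5.8% | 9.1% | 1.61 |

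**3. Power of the treatment-only comparison.** Power = Φ{[|p₁ − p₀|√n − 1.96√(2p̄(1 − p̄))] / √(p₀(1 − p₀) + p₁(1 − p₁))} with n = 331. For the 25% threshold this is Φ{(1.669 − 1.375)/0.698} = Φ(0.42) = 66%. The other two thresholds give 60% and 36%.

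**4. Power with log baseline added.** The documents give no correlation between log baseline and log change, so its size |r| is assumed and varied. Trials were simulated with log change = arm mean + 0.85 × (−|r|·x + √(1 − r²)·e), where x is standardised log baseline and e is standard normal noise. Both logistic models were fitted to each trial and tested by Wald test, with 6,000 trials per row for |r| = 0.2 to 0.7 (Monte Carlo error about √(0.65 × 0.35/6000) = 0.6 points on each power) and 4,000 for |r| = 0.

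| Correlation size (assumed) | 25%: without → with | 50%: without → with | 75%: without → with |
|---|---|---|---|
| 0 | 65.2 → 65.2 | 60.1 → 60.2 | 34.4 → 34.3 |
| 0.2 | 65.8 → 67.1 | 60.4 → 61.5 | 34.8 → 35.0 |
| 0.3 | 66.4 → 68.7 | 61.0 → 62.6 | 34.7 → 35.8 |
| 0.4 | 66.3 → 71.1 | 59.8 → 63.8 | 35.4 → 36.8 |
| 0.5 | 65.7 → 73.2 | 60.2 → 67.1 | 34.8 → 38.6 |
| 0.6 | 65.5 → 77.1 | 60.0 → 70.9 | 35.0 → 40.8 |
| 0.7 | 66.4 → 82.9 | 59.8 → 76.0 | 34.7 → 43.9 |

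A separate simulation of the same model gave gains of about 0–2 points at 0.3, 2–4 at 0.4, and 11, 12 and 5 points for the three thresholds at 0.6. Reading 0.85 as the residual SD, rather than the SD of the change, leaves the gains almost the same: 2.4, 1.1 and 0.6 points at 0.3, and 11.6, 10.5 and 5.8 at 0.6.

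**5. Where the gain comes from.** At a correlation of 0.6:

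| Decline | Model | Odds ratio | SE of log odds ratio | ln(OR)/SE |
|---|---|---|---|---|
| 25% | Treatment only | 1.45 | 0.158 | 2.35 |
| 25% | With log baseline | 1.63 | 0.182 | 2.68 |
| 50% | Treatment only | 1.48 | 0.179 | 2.19 |
| 50% | With log baseline | 1.66 | 0.203 | 2.50 |

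For the 25% threshold, Φ(2.35 − 1.96) = 65% and Φ(2.68 − 1.96) = 76%, in line with the simulated powers. The standard error rises with adjustment. Power rises because the conditional odds ratio lies further from 1 by more than enough to offset that.

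**The case against.** The strongest defence is that nothing here is invalid. Allocation is randomised, so the treatment-only test keeps its error rate, and its interval already allows for chance imbalance in baseline NT-proBNP. A reader might infer from the unstratified randomisation (SAP 1.1) that the odds ratio is biased. It is not. This part of the defence stands.

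Second, a treatment-only model estimates the marginal odds ratio, which is a legitimate target for a responder summary. Adding baseline changes the quantity estimated. This also stands, and it is the one real cost of the change. It also rules out the inference that leaving out baseline widens the interval: step 5 shows that the standard error grows with adjustment.

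Third, no power was promised. The 85% and the 882 belong to the continuous primary endpoint, while the responder models are labelled supportive and carry no decision rule. This stands and keeps the point minor.

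Fourth, a reader might take the unnamed visit as a free choice among Week 4, Week 8 and their average, or nine tests over three thresholds. The documents do not support so strong a reading. The paragraph sits under the analysis of the primary objective, SAP 2.5.1 makes Weeks 4 and 8 the primary time point, and SAP 1.1 repeats this. The average is the natural reading, and a clarifying phrase is enough.

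Finally, only the visible models can be compared. SAP 2.12 refers to a Section 2.13 that is not in the public text.

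**Conclusion.** The point holds as a low-cost improvement. The three responder models omit a covariate that every other visible inferential NT-proBNP model uses, and their test is less powerful than it could be if log baseline is related to log change.

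The size depends on an assumed correlation: no gain at 0, about 0–2 points at 0.3, 2–5 at 0.4, and 11–12 at 0.6 for the 25% and 50% thresholds (5–6 for 75%). It also rests on the design effect, normal log changes and 331 evaluable patients per arm. No single figure should be quoted as the plan's loss or as its upper limit, since a correlation of 0.7 would give about 16–17 points at the lower two thresholds.

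The primary test, its error rate and the sample size of 882 are unaffected.

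**What to change.** In SAP 2.5.4:

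- Add log baseline NT-proBNP as a covariate in all three logistic models.
- Define response on the primary endpoint's ratio: the average of Weeks 4 and 8 divided by baseline, at or below 0.75, 0.50 and 0.25, using the same baseline definition.
- State that the adjusted odds ratio is conditional on baseline. If the marginal odds ratio is also of interest, report the treatment-only result beside it and say in advance which one is the main result.

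The cost is one covariate and a sentence or two of text. No new data are needed. The small downside is in interpretation: the adjusted odds ratio has a larger standard error, lies further from 1, and cannot be compared directly with an unadjusted odds ratio.

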2.6 Analysis of the key secondary objective

No key secondary objective.

2.7 Analysis of secondary objectives

All analyses will be performed on the FAS, unless otherwise specified.

2.7.1 Secondary endpoints

Secondary endpoints include the following:

- The proportional change in NT-proBNP from baseline to Week 8
- Incidence of symptomatic hypotension during 8 weeks of treatment
- Incidence of hyperkalemia (potassium >5.5 mEq/L) during 8 weeks of treatment
- Incidence of angioedema during 8 weeks of treatment
- Biomarkers: hs-Troponin T (high sensitivity), urinary cGMP (UcGMP), UcGMP to urinary creatinine ratio, BNP, NT-proBNP to BNP ratio, and BNP to NT-proBNP ratio at 4 and 8 weeks

Novartis

2.7.2 Statistical hypothesis, model, and method of analysis

For NT-proBNP at Week 8, a proportional change from baseline in a logarithmic scale will be analyzed using an ANCOVA model with treatment as a fixed effect factor and the logarithmic baseline biomarker as a covariate. The estimated treatment effects in terms of ratios of geometric means, based on the LS means from the ANCOVA model, and the corresponding two-sided 95% confidence intervals will be provided. Baseline is Week 0. Week 4 will be used if the Week 8 value is missing.

The incidence of symptomatic hypotension up to Week 8 will be calculated by treatment group. The relative risk (sacubitril/valsartan vs. enalapril) and the 95% confidence interval will also be presented. Similarly, the incidence of hyperkalemia, all angioedema, and positively adjudicated angioedema during the 8 week double-blind phase and the relative risk (sacubitril/valsartan vs. enalapril) will be summarized. Additionally, medication change, lowest documented systolic blood pressure and lowest documented diastolic blood pressure will be summarized by treatment group for symptomatic hypotension. The highest potassium value documented for hyperkalemia will also be summarized by treatment group.

For biomarkers including BNP, BNP to NT-proBNP ratio, NT-proBNP to BNP ratio, hs-Troponin T, UcGMP, and UcGMP to urinary creatinine ratio, the time-averaged proportional change from baseline in a logarithmic scale will be analyzed using an ANCOVA model using data from Weeks 4 and 8 with treatment group as a fixed effect factor and the logarithmic baseline biomarker value as a covariate.

Similar to the primary endpoint, the values from Weeks 4 and 8 will be averaged and the change from baseline will be calculated.

The estimated treatment effect in terms of ratios of geometric means, based on the LS means from the model, and the corresponding two-sided 95% confidence intervals will be presented. The geometric means (presented as a ratio to baseline) will be calculated by exponentially back transforming the LS means based on the ANCOVA model.

For biomarkers including BNP, BNP to NT-proBNP ratio, NT-proBNP to BNP ratio, UcGMP, and UcGMP to urinary creatinine ratio at Weeks 1, 2, 4 and 8, a proportional change from baseline in a logarithmic scale will be analyzed using an ANCOVA model with treatment as a fixed effect factor and the logarithmic baseline biomarker value as a covariate. For each visit, the estimated treatment effects in terms of ratios of the geometric means based on the LS means from the model, and the corresponding two-sided 95% confidence intervals produced from the model will be presented. Similarly, the geometric mean will be calculated by exponentially back transforming the LS means based on the ANCOVA model. This analysis will also be performed for hs-Troponin T at Weeks 1, 4, and 8 (note that hs-Troponin T is not measured at Week 2).

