1.2 Rationale for protocol amendment

Amendment 2 (05Oct2017)

On the basis of blinded review of the projected aggregated (enalapril and sacubitril/valsartan treatment groups combined) rate of missing samples for NTproBNP, this rate exceeds the initial trial assumption of 10%. The sample size has been increased to 882 patients in order to preserve the originally intended power.

Given interest in the effect of sacubitril/valsartan on NTproBNP after titration to dose level 3, a secondary endpoint has been added.

Amendment 1 (28Jul2016)

The protocol inclusion criteria have been modified to be more closely aligned with clinical practice in the United States where patients with acute decompensated heart failure are often rapidly stabilized and transitioned from intravenous to oral diuretic therapy so as to move efficiently to outpatient care, with close follow-up. The protocol has been modified to include patients who are at least 24 hours from hospital presentation versus 48 hours. This change was instituted to allow sites to randomize stabilized patients who otherwise might be discharged earlier than 48 hours. In addition, the window of eligibility, which had been set at 5 days, has been extended to 10 days to permit inclusion of patients who have longer hospitalizations (e.g. due to initial diagnostic uncertainty).

Because a substantial proportion of patients who are stabilized with medical therapy for acute decompensation heart failure are asymptomatic with a systolic blood pressure that remains predominantly within the range of 100 - 110 mm Hg, the inclusion criterion regarding systolic blood pressure has been lowered to ≥ 100 mmHg. The SBP stabilization period was also changed from 24 hours to 6 hours because a 6 hour window is considered an adequate period of time to establish stability.

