5.5.4 Instructions for prescribing and taking study treatment

All medication for the duration of the study will be provided by Novartis. Eligible patients will be randomized via IWRS to either sacubitril/valsartan or enalapril. Patients randomized to the sacubitril/valsartan arm will receive sacubitril/valsartan matching placebo for the first day of treatment to fulfill the required 36 -hour wash-out period (in addition to enalapril matching placebo). Patients randomized to enalapril will not require a washout and will receive active treatment on the first day of treatment, in addition to sacubitril/valsartan matching placebo. The first day of dosing will be provided from a centralized hospital supply containing dose levels 1 and 2 and matching placebos.

From the second day of treatment (third dose), patients will be provided with sufficient medication to last until the next scheduled visit. In order to adequately blind the study, patients will be required to take a total of two tablets (one tablet from the sacubitril/valsartan / sacubitril/valsartan matching placebo pack and one tablet from the enalapril/enalapril matching placebo pack) twice a day for the duration of the study.

Initial dose at randomization will be determined by systolic blood pressure (SBP).

- All patients with a systolic blood pressure (SBP) of ≥100 to ≤120 mm Hg will start at Dose level #1 (2.5 mg Enalapril or 24/26 mg sacubitril/valsartan, BID).
- Patients with a SBP \geq 120 mm Hg will start at dose level #2 (5 mg enalapril or 49/51 mg sacubitril/valsartan, BID).
- Patients will be titrated to the next dose level at Weeks 1 and 2 (Visits 3 and 4) with the goal of reaching the target dose for dose level #3 (10 mg enalapril or 97/103 mg sacubitril/valsartan, BID) by week 2 (Visit 4).
- Patients should be titrated to the next dose level at week 1 only if their SBP is >110 mm Hg and at week 2 if their SBP is > 100 mm Hg.

Table 5-3	Dose titration schedule based on SBP			
Visit	Previous dose level	Systolic Blood pressure mm Hg*	Start/remain/tit rate to: Dose level #	
Baseline (Visit 2)	N/A	≥ 100	1	
	N/A	≥120	2	
1 Week (Visit 3)**	1	<110	1	
		≥110	2	
	2	<110	2	
	2	≥110	3	
2 weeks (Visit 4)	1	<100	1	
	I	≥100	2	
	2	<100	2	
	2	≥100	3	

Dose titration will proceed according to the following table:

Novartis Amended Protocol Version 02 (Clean) Page 36 Protocol No. CLCZ696BUS01

Visit	Previous dose level	Systolic Blood pressure mm Hg*	Start/remain/tit rate to: Dose level #

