2.4.1 Study treatment / compliance

The duration of double-blind study treatment phase is defined as:

Duration (days) = (date of last study treatment in double-blind study phase - date of first study treatment) +1

The first date of study treatment is recorded on the Dose Administration (Visit 2) eCRF.

The duration of the open-label study treatment phase is defined as:

Duration (days) = (date of last study treatment in open-label study phase - date of first study treatment in open-label phase) +1

The duration of the pooled phase (sacubitril/valsartan in double-blind phase and/or sacubitril/valsartan in open-label phase) is defined as:

Duration (days) = (date of last study treatment of sacubitril/valsartan [any phase] - date of first study treatment of sacubitril/valsartan [any phase]) +1

Summary statistics will be displayed for the duration of double-blind study treatment, duration of open-label study treatment and duration of pooled sacubitril/valsartan by phase.

The durations will also be categorized into weekly time intervals (<7 days, 7 - <14 days, 14 - <21 days, ..., etc.). The number and percentage of patients in each category will be presented by phase.

Total patient-days of exposure will also be summarized by phase.

In addition, the number and percentages of each dose level dispensed by visit will be summarized by treatment group and open-label sacubitril/valsartan. The number and percentage of the maximum dose levels dispensed will also be presented by treatment group and open-label sacubitril/valsartan. Similarly, the up-titrated doses, down-titrated doses and unchanged doses will be summarized by visit, treatment group and open-label sacubitril/valsartan. The number and percentage of patients who were dispensed dose level 3 by Week 6 will be summarized by treatment group.

An additional summary of patient dose level and titration data will be generated by visit and systolic blood pressure using the visit-specific systolic blood pressure cut-off values from the dose titration schedule.

All information on dose administration will be listed.

2.4.2 **Prior**, concomitant and post therapies

Non-HF Medications

Prior and concomitant non-HF medications will be coded according to the World Health Organization (WHO) Drug Reference List (v15.3 or later). Prior and concomitant medications are mutually exclusive, as defined below:

- Prior medications are defined as any medication with an end date prior to the first dose of study treatment

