2.7.3 Handling of missing values/censoring/discontinuations

The analysis will be performed based on all available data in the FAS and based on likelihood method with an assumption of missing at random for missing data.

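### The SAP carries Week 4 NT-proBNP into a missing Week 8 value while its missing-data rule for the same endpoint is likelihood under missing at random with no exception; the fill can bias the Week 8 ratio either way

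*SAP*

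**What the plan says.** SAP 2.7.2 analyses the log change in NT-proBNP from baseline to Week 8 with a one-visit ANCOVA (treatment, log baseline) and adds "Week 4 will be used if the Week 8 value is missing". The protocol synopsis and Protocol 9.5.1 carry the same rule.

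SAP 2.7.3 covers missing values for the secondary objectives. It uses all available FAS data and is "based on likelihood method with an assumption of missing at random for missing data". It does not mention the fill. In the protocol the likelihood sentence stands in 9.4.3, under the primary variable only, so the overlap on this endpoint arises in the SAP. SAP Section 4 does not list it among the changes from the protocol.

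Two other planned Week 8 analyses state no fill:

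- SAP 2.5.4, supportive: "For NT-proBNP at Weeks 4 and 8, a proportional change from baseline in a logarithmic scale will be analyzed".
- SAP 2.7.2, further down, for BNP and the BNP/NT-proBNP ratios among others: "ratio at Weeks 1, 2, 4 and 8, a proportional change from baseline in a logarithmic scale".

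Protocol 1.2 gives the endpoint's purpose: "Given interest in the effect of sacubitril/valsartan on NTproBNP after titration to dose level 3, a secondary endpoint has been added".

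**The concern.** Under 2.7.2 a patient without a Week 8 sample enters the model with a Week 4 value counted as a Week 8 observation. Under 2.7.3 the same value stays missing and the model deals with it. The SAP does not say that one rule overrides the other, or that they apply in sequence. Together with the no-fill ANCOVA in 2.5.4, more than one Week 8 ratio could be reported with no stated rule for which is the main one. Week 8 NT-proBNP could also rest on a different set of patients from its own ratio to BNP.

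The fill also sits uneasily with the endpoint's purpose. Protocol 5.5.4 titrates at Weeks 1 and 2 "with the goal of reaching the target dose for dose level #3" by Week 2, so for many patients a Week 4 sample already follows level 3. But Protocol Table 5-3 still allows steps up at Weeks 4 and 6, and SAP 2.4.1 plans that "The number and percentage of patients who were dispensed dose level 3 by Week 6 will be summarized by treatment group". For some patients the substituted sample therefore predates a titration step.

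The extent of filling would not be visible in a planned table. The one summary of this kind in SAP 2.5.4 is "A descriptive summary of patient evaluability for the primary endpoint analysis", which does not cover the Week 8 endpoint.

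**Working it through.** **The plan's own figure.** Protocol 9.7 and SAP Section 3 give a ratio of 0.82, log-scale SD 0.85, two-sided alpha 0.05, 85% power and 25% non-evaluable. Per arm n = 2 × (1.960 + 1.036)² × 0.85² / (ln 0.82)² = 330, so 660 in total and 660/0.75 = 880. The t-based version gives 331 per arm, and 662/0.75 = 882.7. The stated 882 reproduces. It belongs to the primary endpoint; the documents give no power or missing rate for Week 8 alone. For scale, the planning standard error of the log ratio is 0.85 × √(2/331) = 0.066.

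**Equal filling in both arms.** Let R4 and R8 be the true treatment ratios at Weeks 4 and 8, and m the share of Week 8 values filled. When filling is unrelated to the values, the expected ratio is

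R(filled) = exp[(1 − m) ln R8 + m ln R4].

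The share m (5-20%) is an assumption. So are R4 and R8, except in the second row, which uses the 26% (Week 4) and 25% (Month 8) reductions quoted in Protocol 9.7.

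| R4 / R8 | Filled ratio, m = 5% to 20% | Shift as share of log effect | Direction |
|---|---|---|---|
| 0.82 / 0.82 | 0.82 | 0 | none |
| 0.74 / 0.75 | 0.7495 to 0.748 | under 1% | away from null |
| 0.87 / 0.773 | 0.778 to 0.792 | 2% to 9% | toward null |
| 0.90 / 0.75 | 0.757 to 0.778 | 3% to 13% | toward null |
| 0.773 / 0.87 | 0.865 to 0.850 | 4% to 17% | away from null |

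Example: 0.75 × (0.90/0.75)^0.20 = 0.778. The log shift is 0.20 × ln 1.2 = 0.0365, or 0.0365/0.066 = 0.55 standard errors. Across the 0.87/0.773 and 0.90/0.75 rows the shifts run from 0.09 to 0.55 standard errors.

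**Unequal filling.** Suppose the ratio is 0.82 at both visits but levels in both arms are 1.2 times as high at Week 4 as at Week 8 (assumed). The expected ratio is then 0.82 × 1.2^(mS − mE), where mS and mE are the shares filled on sacubitril/valsartan and enalapril.

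- 10% vs 15% filled: 0.813; reversed, 0.828.
- 10% vs 20% filled: 0.805; reversed, 0.835.

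**Missingness that depends on the Week 4 value.** Simulation settings, all assumed except the SD and the 441 per arm (882/2): 2,000 trials; complete baseline and Week 4 samples; total SD of log change 0.85; baseline log SD 1 and slope −0.3; residual correlation between visits 0.7; level ratio 1.2; log-odds of a missing Week 8 value rising by 0.5 per SD of the Week 4 log change; true ratio 0.82. The likelihood contrast regresses Week 4 on treatment and baseline in all patients and Week 8 on treatment, baseline and Week 4 in those observed. It equals the direct treatment coefficient plus the Week 4 coefficient times the Week 4 treatment effect.

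| Missing, sac/val vs enalapril | Fill | Observed-case ANCOVA | Likelihood |
|---|---|---|---|
| 10% vs 15% | 0.809 | 0.830 | 0.820 |
| 15% vs 10% | 0.831 | 0.810 | 0.820 |

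A rerun agreed to within 0.001. The fill and the observed-case analysis err in opposite directions here, so deleting the fill sentence alone would not solve the problem.

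**Precision.** With random missingness and visit correlation 0.5-0.9, the mean standard error at 10% missing is 0.0537 with the fill and 0.0541-0.0558 with likelihood. At 20% missing it is 0.0538 and 0.0548-0.0584. The fill's standard error is thus 1-4% smaller at 10% and 2-8% smaller at 20%, because filled values count as Week 8 data. These are below 0.066 because they use 441 per arm and adjust for baseline.

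**The case against.** The best reply is that a specific rule governs over a general one. The fill is stated consistently in the protocol synopsis, Protocol 9.5.1 and SAP 2.7.2, while 2.7.3 repeats the primary endpoint's sentence word for word. The two could also work in sequence: fill where Week 4 exists, then fit what is available. Either reading is possible, but the SAP states neither. Even if the fill governs, it remains a carry-forward that counts Week 4 data as Week 8 data.

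Other points stand and limit the weight of this one:

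- The only early and late effects in the documents give a negligible shift; every larger figure rests on assumed inputs.
- 20% filled is generous. The planned 25% covers all non-evaluable samples for the primary endpoint, whereas a fill needs baseline and Week 4 present and Week 8 absent.
- The simulation meets the conditions that the likelihood contrast needs. In separate runs where missingness depended on Week 4 in one arm only, the fill (0.805 or 0.840 for a true 0.82) was closer than the observed-case analysis (0.867 or 0.779). That counts against simply deleting the fill. The joint likelihood estimate in those runs was 0.821 or 0.823.
- SAP 2.7.3 does not itself name a repeated-measures model. That model is one concrete way to carry out its rule.
- The no-fill ANCOVA in SAP 2.5.4 gives a partial check on the fill, and the number filled could be derived from the listings.
- There is no key secondary objective, and this endpoint is reported as an estimate with a confidence interval.

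**Conclusion.** The concern holds. Two missing-data rules cover one endpoint in the SAP with no stated order, and the fill can move the Week 8 ratio in either direction. The bias is zero when the Week 4 and Week 8 effects are equal and filling is balanced. It is toward the null when the Week 4 effect is smaller and away from it when larger. It also arises when levels change between visits and the arms are filled unequally.

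The likely size is small to moderate: from under 1% of the log effect to 13-17% in the steepest cases examined, at most 20% filled. The documents give neither the Week 8 missing rate by arm nor the course from Week 4 to Week 8 in this population, so the actual direction and size are unknown. The case for acting rests mainly on fixing the main Week 8 analysis before unblinding. This is a point the sponsor should address; it does not threaten the primary result.

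**What to change.** Replace the fill sentence in SAP 2.7.2 with wording such as:

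> Log change from baseline at Weeks 4 and 8 will be analysed with a repeated-measures likelihood model with treatment, visit, treatment-by-visit, log baseline and baseline-by-visit terms and an unstructured covariance. The back-transformed Week 8 treatment contrast with its 95% confidence interval is the main result.

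Then:

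- keep the Week 4 fill as a labelled sensitivity analysis;
- label the Week 8 ANCOVA in SAP 2.5.4 as observed-case;
- report the number of Week 8 values filled per arm, beside the count of deaths before the Week 8 window that SAP 2.3.1 already plans;
- list the change from Protocol 9.5.1 in SAP Section 4.

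If the sponsor keeps the fill as the main analysis, SAP 2.7.3 must name it as an exception.

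The cost is SAP wording and one PROC MIXED model, with no new data. The interval would be about 1-4% wider than with the fill at 10% missing and 2-9% wider at 20%, and there would be a protocol difference to list. The model relies on missing at random and does not settle how deaths should be handled. It also cannot recover samples left unanalysed after consent is withdrawn (SAP 2.12); no method can.
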